# 7 Sample Size

With 23 clusters per arm and an average of 20 patients per cluster, assuming an intra-class correlation of 0.03, a typical coefficient of variation of the cluster size of 0.65 (Campbell, 2014), and 2.5% significance (adjusted to 2.5% because of the use of two co-primary outcomes), we would be able to detect an effect size of 0.33 with at least 90% power on the co-primary outcomes (emotion and handicap sub-scales of the Stroke Impact Scale (SIS v3.0)). The sample size calculation has been inflated to allow for a rate of 20% loss to follow-up for patients within clusters. Loss to follow-up of entire clusters is not anticipated.

The conservative estimate of 20 patients per practice is drawn from the trials pilot data (unpublished) and the research groups experiences of running previous trials in this population (Fletcher K, 2010; Fletcher K, 2010; O'Brien C, 2013). A typical practice with a list size of between 7,000 to 10,000 will have approximately 100 - 150 patients on the stroke register (Progress in improving stroke care, 2010). We anticipate that the electronic search applying the exclusion criteria will eliminate around 40% of these (based on the pilot study) leaving 60 – 90 eligible patients per practice, of which about 30% will agree to take part (18 – 27 per practice). This will yield between 16 – 24 participants per practice.

The IPCAS trial was powered based upon the two co-primary outcomes (SIS emotional and handicap domains). It is important to be aware that the trial was not powered based on any secondary or exploratory end-points, and this should be considered in particular when interpreting any resulting p-values.

# 8 General Considerations

# 8.1 Timing of Analyses

The final statistical analysis will be performed after all patients have completed their 12 month follow-up or have dropped out of the trial. The final statistical analysis will be performed on data that has been cleaned and hard locked. The final statistical analysis should only be performed after the finalisation and approval of this SAP document.

# 8.2 Analysis Populations

Patients may be included or excluded from particular analysis populations on the basis of certain characteristics or criteria. These are detailed below.

#### 8.2.1 Full Analysis Population

The full analysis population, also often referred to as the "intention-to-treat" population, comprises all randomised general practices and consented patients within them, regardless of eligibility error, post-randomisation withdrawal, and whether the assigned treatment was received, with sufficient or insufficient compliance. Any analyses will be based on the treatment arm assigned at randomisation, regardless of what treatment was actually received.

A subset of the full analysis population will be used to analyse the two co-primary efficacy end-points, including only the patients with the necessary data available at baseline and twelve months.

The full analysis population will also be used to analyse several secondary and exploratory end-points as outlined elsewhere in this SAP, some of which, like the primary efficacy analyses, may require data to be complete at particular time points and therefore will only include a subset of the full analysis population with the necessary data available.

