9.1. Baseline Data Collection

The primary outcome data will be collected via postal questionnaire at the time of invite to the study prior to Practice randomisation. Secondary outcome data (SIS Short Form, EuroQol EQ-5D-5L, and ICEpop CAPability measure for Adults (ICECAP-A)) will also be collected by postal questionnaire after randomisation. Non-responders to the secondary outcome questionnaire will be followed-up by telephone. Where a patient has difficulty completing a questionnaire because of physical or communication difficulties, they will be encouraged to seek the help of a carer.

Demographic data including age, ethnicity, gender, time since stroke, partial post code, and co-morbidity and medication use (prescription & 'Over the Counter', OTC) will also be collected at baseline.

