10.2. Analysis of Primary Outcome

We will use intention to treat (ITT) methods for the analysis of the primary end-points. A mixed effects model will be used to model each of the co-primary outcomes with a cluster random effect and fixed effects for the intervention and covariates that might potentially confound the relationship. Distributional assumptions will be assessed graphically by residual q-q plots and residual by fitted value plots. To handle the co-primary outcomes, 97.5% confidence intervals will be reported for the two primary treatment effects which are equivalent to having the Bonferonni correction on the planned 5% significance level for a single endpoint.

The missing data will be analysed under the assumptions of missing completely at random and missing at random. Multiple imputation will be used to impute missing outcome data and the various potential predictors of missingness will be included in the imputation model. Additionally, a sensitivity analysis may be used to investigate non-ignorable missingness mechanisms and their influence on the results.

The full details of the statistical analysis will be specified in the statistical analysis plan (SAP).

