# **10.1 Primary Efficacy Analyses**

The standardised domain total scores will be calculated (as described in section 9.2.1) for each of the two co-primary outcomes (SIS emotional domain and SIS handicap domain). The analyses will focus on the evidence for a difference in SIS score (handicap or emotion) between the intervention and control group.

Each domain will be modelled separately and the following model fitted:

$$Y_i = \beta_0 X_{0i} + \beta_1 X_{1i} + \epsilon_i$$

For each co-primary outcome there is the potential for clustering and therefore a mixed effect model will be fitted with a random effect for general practice and fixed effects for the treatment group to assess the effect of clustering:

$$Y_{ij} = \beta_0 X_{0ij} + \beta_1 X_{1ij} + u_j + \epsilon_{ij}$$

Where,

Yij = continuous outcome SIS score (emotion/ handicap domain)

*i* = individual patient

j = cluster/ practice

 $X_1$  = dummy variable for the intervention treatment group.

X0 = baseline covariates (baseline score, gender, cluster size, time since last stroke at consent)

 $\beta_0$  = intercept which represents the population average SIS score

 $\beta_1$  = difference in score between intervention and control groups at 12 months

 $u_i \sim N_1(0, \sigma_h^2)$  is the cluster-level random practice effect

 $\epsilon_{ii} \sim N_1(0, \sigma_e^2)$  is the residual error

There is an a priori hypothesis that the following covariates may be associated with the co-primary outcomes: gender, age at baseline (categorical), time since last stroke (categorical), general practice list size (the stratifying variable used in the randomisation, split into two categories; <10,500 and  $\geq$ 10,500 patients) and deprivation score (continuous, both at the patient and practice level). Once the primary analysis model is decided, these covariates will be added to assess and changes in treatment effect on the co-primary outcomes.

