Each data point will be assumed to have an error term that is identically and independently normally distributed with constant variance. These assumptions will be checked using histograms and box plots to look at the distributional form of the primary outcome SIS scores. All assumptions for the linear mixed effects models will be assessed by viewing plots of the residual values and QQ plots. If any of the assumptions of the linear mixed model are violated then the dependent variable, SIS score, may be transformed to normality or if this fails to correct the distributional assumptions, non-Gaussian or semi/non-parametric methods for analysis will be used.

 $Y_{ijk} = \beta_0 X_{0ij} + \beta_1 X_{1ij6} + \beta_2 X_{1ij12} + u_j + \varepsilon_{ijk}$ 

The analysis population for the primary outcome will be all patients with 12-month outcome measure as the mixed effects model assumes missing at random (MAR).

For missing data analysis the following model will be fitted if there is a cluster effect:

Yijk = continuous outcome SIS score (emotion/ handicap domain)

*i* = individual patient

j = cluster/ practice

*k* = 6 month and 12 follow-up scores

 $X_1$  = dummy variable for the intervention treatment group.

X0 = baseline covariates (baseline score, gender, cluster size, time since last stroke at consent)

 $\beta_0$  = intercept which represents the average baseline SIS score for person *i* 

 $\beta_1$  = difference in score between intervention and control groups at 6 months

 $\beta_2$  = difference in score between intervention and control groups at 12 months (primary)

 $u_i \sim N_1(0, \sigma_b^2)$  is the cluster-level random practice effect

$$\begin{pmatrix} Y_{ij0} \\ Y_{ij6} \\ Y_{ij12} \end{pmatrix} \sim MuN \begin{pmatrix} \beta_0 \\ \beta_0 + \beta_1 + X_{ij6} \\ \beta_0 + \beta_2 + X_{ij12} \end{pmatrix}$$

$$\epsilon_{ijk} \sim MuN \begin{pmatrix} 0 \\ 0, \Sigma_0 \\ 0 \end{pmatrix}$$
 is the residual error, and  $\Sigma_0$  initially has an AR1 structure.

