# 11 Missing Data

The primary analysis will be the ITT participants who are in the primary analysis population. Linear mixed effects models will be used to analyse the co-primary end-points that are repeated measured. One key benefit of mixed effect models is that this type of model can include data from incomplete cases, so missing data does not necessarily preclude a subject's data from the analysis. In this instance, missing data will be dealt with using a missing at random (MAR) assumption on the analysis population. The outcome variable will include baseline, 6months and 12months outcomes. The mixed effect model will have participant id as a random effect (i.e. random baseline) and the fixed factors will be time, included as a factor variable, and treatment indicator. To help the MAR assumption the residuals of the model will be assumed to have autocorrelation (if the data allow an unstructured correlation structure stratified by treatment indicator). Additional baseline covariates will be included in the model that are potential confounders.

If there is a large amount of missing outcome data from the questionnaires, we will do a sensitivity analysis missing outcome data for the primary analysis as described in White et al. (2011) and Sullivan *et al* (2018). For each questionnaire, where guidelines exist for missing data, they will be followed (see Section 11.1).

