# **12** Sensitivity Analyses

To account for COVID-19 effects of the UK lockdown (on Monday 23rd March 202) during part of the study, a patient-level binary factor for this will be created by using the date of the 12-month assessment relative to this. As both co-primary endpoints of "emotion" and "handicap" (i.e. participation) may be affected by this event, a sensitivity analysis will be conducted by repeating the primary analyses but now including this new variable.

As a sensitivity analysis, the co-primary end-points will also be analysed under the assumption that missing data is either "missing completely at random" or "missing at random". In this instance, multiple imputation will be used to impute missing outcome data and the various potential predictors of missingness will be included in the imputation model.

Multiple imputation for cluster randomised trials should be based on a multilevel imputation model (Karla Diaz-Ordaz, 2014). For example, missing data will be imputed under different assumptions such as X=4 or X=5 and the primary analysis repeated to check the impact of this. Altering X to be different values: 5,6,7,8. Will eventually mean a "significant" result disappears and that might happen at say 7, which is the tipping point.

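### The SAP defines the co-primary analysis set inconsistently and gives no rule for a missing baseline score, so observed 12-month scores can be dropped

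*SAP*

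**What the plan says.** Three sections of the SAP bear on who enters the co-primary analysis.

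- **Section 8.2.1** defines the full analysis population by intention to treat. For the co-primary end-points it then takes a subset, "including only the patients with the necessary data available at baseline and twelve months".
- **Section 10.1** states: "The analysis population for the primary outcome will be all patients with 12-month outcome measure". It sets no baseline condition. Its model nevertheless has the baseline score and time since last stroke among the fixed covariates X0, with gender and cluster size.
- **Section 11** describes a repeated-measures model: "The outcome variable will include baseline, 6months and 12months outcomes". It adds that in such a model "missing data does not necessarily preclude a subject's data from the analysis".

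On filling gaps, section 12 says that "multiple imputation will be used to impute missing outcome data", and Protocol 10.2 likewise applies imputation to outcomes. Neither document says what happens when a baseline score is missing. SAP 9.2.1 scores each SIS domain as a sum of items and gives no rule for a skipped item.

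The protocol's principle is plain: "We will use intention to treat (ITT) methods for the analysis of the primary end-points". On timing, Protocol 9.1 says of the baseline SIS domains: "The primary outcome data will be collected via postal questionnaire at the time of invite to the study prior to Practice randomisation". Protocol 18.1 indicates that this questionnaire comes back with the consent form.

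**The concern.** A patient whose 12-month score was observed has supplied the quantity the trial is about. Dropping that patient because a baseline item was left blank discards a real outcome, on top of the 20% loss to follow-up already allowed for, and moves away from the protocol's intention-to-treat commitment.

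The exclusion also gains nothing. The baseline score was collected before the practice was allocated, so a gap in it can be filled without reference to arm and without biasing the comparison.

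Choosing the section 10.1 definition does not settle the matter on its own. Standard mixed-model software deletes any record with a missing covariate, so the baseline condition returns through X0 unless a rule for missing baseline is written down. As the plan stands, the choice of analysis set stays open until the data are in hand.

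**Working it through.** **1. The definitions side by side, for a patient with a 12-month score and no usable baseline score**

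| SAP text | Patient kept? |
|---|---|
| 8.2.1, population | No |
| 10.1, population | Yes |
| 10.1, primary model, standard fit | No, because X0 contains the baseline score |
| 10.1, missing-data model with 6 and 12 months | Unclear: a joint distribution for baseline, 6 and 12 months is shown, but X0 still lists the baseline score |
| 11, baseline in the outcome vector | Yes |
| 12, multiple imputation | No rule; the stated target is missing outcomes |

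**2. Inputs from SAP section 7**

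23 practices per arm, mean 20 patients per practice, intraclass correlation (ICC) 0.03, coefficient of variation of cluster size (CV) 0.65, significance level 0.025, effect size 0.33 SD, 20% loss within practices. The level is taken as two-sided, which the SAP does not state.

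**3. Reproducing the stated power**

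With m analysed patients per practice:

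- Design effect DE = 1 + ((1 + CV²)m − 1) × ICC, where 1 + 0.65² = 1.4225
- Effective number per arm = 23m/DE
- SE = √(2 / effective number)
- Power = Φ(0.33/SE − 2.241)

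Before loss, m = 20: DE = 1 + (28.45 − 1) × 0.03 = 1.824; effective number 460/1.824 = 252.3; power 92.9%.

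After 20% loss, m = 16: DE = 1 + (22.76 − 1) × 0.03 = 1.653; effective number 368/1.653 = 222.7; SE 0.0948; power 89.3%. This is close to the stated figure of at least 90%, and I take that figure as reproduced.

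**4. Adding the baseline condition**

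Let p be the share of patients with a 12-month score who lack a usable baseline. The documents give no value, so p is an assumed range. Then m = 16(1 − p), and the full set is 920 × 0.8 = 736 patients.

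| p | Lost | Analysed | Power |
|---|---|---|---|
| 0 | 0 | 736 | 89.3% |
| 1% | 7 | 729 | 89.1% |
| 2% | 15 | 721 | 88.9% |
| 5% | 37 | 699 | 88.3% |
| 10% | 74 | 662 | 87.1% |

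The SE at 5% and 10% is 0.0962 and 0.0978, against 0.0948: a rise of 1.5% and 3.2%. With a t reference on 44 degrees of freedom the power is 87.3%, 86.2% and 85.0% at p = 0, 5% and 10%, so the drop is much the same.

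**5. Why these losses are an upper bound**

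The calculation treats each dropped patient as carrying full information. In a baseline-adjusted model, a patient without baseline carries about 1 − r² as much as one with it, where r is the baseline to 12-month correlation (assumed, not given). At individual level, dropping rather than keeping these patients multiplies the variance by ((1 − p) + p(1 − r²))/(1 − p). At p = 5% this is (0.95 + 0.0455)/0.95 = 1.048 for r = 0.3, and (0.95 + 0.0255)/0.95 = 1.027 for r = 0.7.

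**6. What p might be**

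If one skipped item voids the nine-item emotion domain, and items are skipped independently at 0.5% to 1% (both assumptions), the incomplete share is 1 − 0.995⁹ = 4.4% to 1 − 0.99⁹ = 8.6%. The 10% row lies above that range.

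**The case against.** The strongest reply is that section 8.2.1 is not the SAP's settled rule. Section 10.1 is the more specific text and has no baseline condition, and section 11 offers a model in which a patient without baseline can stay. A reader of 8.2.1 alone might infer that the plan definitely removes these patients and that nothing in it could bring them back. The documents do not support that reading. What stands is that the three sections disagree and that the section 10.1 model, as written, has no rule for a missing baseline score.

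The second reply is that few patients are affected. The baseline SIS comes back with consent, so a wholly missing form should be rare and the gaps are mainly skipped items. The 4.4% to 8.6% range is fragile. SAP 9.2.1 does not say that one missing item voids a domain. Section 11 says questionnaire guidelines will be followed where they exist. Skipped items tend to cluster in the same people, and only patients with a usable 12-month score count. All of this stands, and it is why the size is given as a range of assumed rates.

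A reader might also infer that those dropped would be mostly patients with communication or cognitive difficulty, and hence that the result would be biased. No passage shows who leaves items blank, and Protocol 9.1 encourages help from a carer. Restricting on completeness fixed before allocation does not in itself bias the comparison between arms.

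**Conclusion.** The concern holds as an inconsistency with a modest cost. Sections 8.2.1, 10.1 and 11 define the co-primary set in ways that cannot all be followed, and no rule covers a missing baseline score. Following 8.2.1, or fitting the 10.1 model in the standard way, discards observed 12-month scores.

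The loss is at most about 1 power point if 5% of patients with a 12-month score lack baseline, and about 2 points if 10% do. It is smaller to the extent that baseline predicts outcome. No figure in the documents is wrong on this point.

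The conclusion rests on the assumed rates, on a two-sided 2.5% level, and on Protocol 9.1's statement that the baseline SIS precedes practice randomisation. That timing is documented for the baseline SIS only. For time since stroke the documents say it is collected at baseline, without placing it before or after allocation, so the argument for arm-blind completion does not carry over to it automatically.

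**What to change.** 1. Use one co-primary set: all consented patients in randomised practices with a 12-month score on the domain analysed. Delete 'baseline and' from the subset sentence in 8.2.1, and align 10.1 and 11 with this definition.
2. In the section 10.1 primary model, replace a missing baseline SIS score by the mean over both arms and add a missing indicator. Modelling baseline as an outcome, as section 11 already describes, is an acceptable alternative. Name one of the two before the data are analysed.
3. Give time since stroke an 'unknown' level only if its recording can be shown not to depend on allocation.
4. The deprivation score needs a rule only for the later covariate-adjusted model, because it is not in X0 in section 10.1. Section 8.3 lists it for the co-primary models and should be brought into line.

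The cost is a few sentences in the SAP, a few lines of code, and slightly less adjustment for the patients whose baseline is filled in.

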#### 8.2.2 Per Protocol Population

A per protocol analysis population typically includes only the subjects (in this case including both general practices and patients) who adhered to the study protocol, including full compliance with the assigned treatment regime and scheduled follow-up. Given the difficulty in measuring compliance to intervention arm treatment, as it is a package of care with several optional components, a per protocol population will not be defined. Instead, intervention fidelity will be assessed to examine how well the intervention was implemented as planned (see Section 9.4 and 14).

#### 8.2.3 Safety Population

The safety population comprises all consented patients, regardless of whether they received any study intervention, including control, and regardless of length of time in the study. The safety population will be used to provide summary statistics on adverse events.

# 8.3 Covariates and Subgroups

As the randomisation for the IPCAS trial is stratified by general practice list size (Strata 1: General practice list size less than 10,500 patients; Strata 2: General practice list size equal to or greater than 10,500 patients). There is an *a priori* hypothesis that smaller practices can deliver the intervention more successfully due to more personal care, therefore general practice list size will be adjusted for in the secondary analyses using the same category levels as used in the randomisation. This will be included as a cluster-level fixed effect in the mixed effect models for the analyses of the two coprimary end-points.

Various subject-level covariates are considered as important baseline covariates or clinically significant in this study. These subject-level and cluster-level covariates will be included as subject-level or cluster-level fixed effects in the mixed effects model for the analyses of the two co-primary end-points, and in the mixed effect models of secondary end-points where deemed appropriate:

- Baseline categorical variable gender (male/female).
- Age at baseline in the following categories: 20-64, 65-74, 75-84, 85+ years.
- Time since last stoke at baseline in the following categories: 0-6months, 6 months-1year, 1-2 years, 2-5 years, 5-10years, 10 years +.
- Deprivation score (subject and practice).

#### 8.4 Interim Analyses and Data Monitoring

#### 8.4.1 Interim Analyses

No formal interim analyses are planned.

#### 8.4.2 Data Monitoring

Oversight of the trial will fall to an independent committee fulfilling the combined roles of trial steering committee (TSC) and Data Monitoring Committee (DMC). They will provide overall supervision of the conduct of the trial. The committee will consider relevant factors in interim decision-making such as recruitment rate and completion schedule, baseline comparability across treatment arms, data completeness and follow-up, safety profile and ethical issues. Initially, the TSC/DMC will meet after the first 100 participants are recruited, then 6-monthly. This frequency may increase or decrease according to need. The statistician will be involved in producing data monitoring reports.

A snapshot of the data used for each analysis, including that for data monitoring reports, should be preserved by the data manager. The statistician will also maintain a separate copy of the data files provided for each analysis, including that for data monitoring reports, and will also maintain a copy of all programming code and analysis reports provided by the statistician to the data monitoring committee and/or trial team.

Analyses performed for data monitoring purposes will not include efficacy analyses. In order to minimise bias, only the final analyses will include efficacy analyses. This is particularly important given that the IPCAS trial is open-label.

